7.6.2 Analysis

No statistical tests will be performed.

7.6.3 Presentation

The total score of SIRS will be presented using summary statistics.

7.7 Secondary Endpoints – Organ failure

7.7.1 Definition

Respiratory Failure

The presence of respiratory failure will be assessed on Days 1-10.

Respiratory failure is defined as $\text{PaO}_2/\text{FiO}_2 \leq 300$, either determined by ABG or calculated from the $\text{SpO}_2/\text{FiO}_2$ or the use of non-invasive or invasive mechanical ventilation (respiratory support).

Renal Failure

- An increase in serum creatinine $\geq 300\%$ if the baseline creatinine is known from prior to the hospitalization for acute pancreatitis, or
- A serum creatinine ≥ 1.9 mg/dL, or
- The initiation of renal replacement therapy

For patients with pre-existing chronic kidney disease, organ failure will be defined as:

- An increase in serum creatinine $\geq 300\%$ if the baseline creatinine is known from prior to the hospitalization for acute pancreatitis, or
- An increase of serum creatinine to a level >4.0 mg/dl, or

- The initiation of renal replacement therapy

Cardiovascular Failure

The presence of cardiovascular failure will be assessed on Days 1-10. For the cardiovascular system, organ failure will be defined as:

- A systolic blood pressure <90 mmHg that is not fluid responsive, or
- The use of either vasopressor or inotropic support

Any Organ Failure

If the patient meets the conditions for at least one type of organ failure (respiratory failure, renal failure or cardiovascular failure), they have a diagnosis of Organ Failure. If they meet the conditions for more than one organ failure they also have a diagnosis of multiple organ failure. Patients free from all types of organ failure or without data to support diagnosis of organ failure, do not have organ failure

Transient organ failure

Patients with transient organ failure are identified by organ failure lasting less than 48 hours. Persistent organ failure is documented for greater or equal to 48 hours. New persistent Organ Failure is only applicable for patients without Organ Failure at baseline.

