#### **8.11.11 Biomarker Analysis**

For biomarker testing, serum and urine samples will be collected on Days 1 – 10 and sent to the central lab. The date and time of the blood and urine samples should be recorded. Serum biomarkers planned for testing include C-Reactive Protein (CRP), D-Dimer, procalcitonin, Il-6 and Il-8. Urine NGAL will also be tested. Results will not be provided to the PI or treating physician.

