## Appendix 1 Definition of Organ Failure

The definition of organ failure encompasses three organ systems, respiratory system, renal system and cardiovascular system.

For the respiratory system, organ failure will be defined as:

- PaO2/FiO2 ≤300, or
- SpO2/FiO2 ≤315, or
- The use of noninvasive or invasive mechanical ventilation

For the renal system, in patients without known chronic kidney disease, organ failure will be defined as:

- An increase in serum creatinine ≥300% if the baseline creatinine is known from prior to the hospitalization for acute pancreatitis, or
- A serum creatinine ≥1.9 mg/dL, or
- Urine output of <0.3 mL/kg/hour for ≥24 hours or anuria for ≥12 hours, or
- The initiation of renal replacement therapy

For patients with pre-existing chronic kidney disease (baseline GFR <60 mL/min/1.73 m^2), organ failure will be defined as:

- An increase in serum creatinine ≥300% if the baseline creatinine is known from prior to the hospitalization for acute pancreatitis, or
- An increase of serum creatinine to a level >4.0 mg/dl, or
- Urine output of <0.3 mL/kg/hour for ≥24 hours or anuria for ≥12 hours, or
- The initiation of renal replacement therapy

For the cardiovascular system, organ failure will be defined as:

- A systolic blood pressure <90 mmHg that is not fluid responsive, or
- The use of either vasopressor or inotropic support

The presence of organ failure will be assessed on Days 1-10.

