2 INTRODUCTION

This Statistical Analysis Plan (SAP) gives details regarding the statistical analyses and data presentation outlined in the final Clinical study protocol (CSP) for the study *CM4620-201*. Any changes from the final CSP are given in Section 8. This needs to be approved and signed prior to database lock.

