7.5 Secondary Endpoints - Biomarker

7.5.1 Definition

The following biomarkers will be used in the analyses.

ANC/ALC (Absolute neutrophils count / Absolute Lymphocytes count)

C-Reactive Protein (CRP)

D-Dimer

Procalcitonin

Il-6

Il-8

Absolute and percent change will be calculated for each biomarker.

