7.8 Secondary Endpoints – SOFA score

7.8.1 Definition

The total SOFA score will be calculated using all including parts:

Respiration Score, Coagulation Score, Liver Score, Cardiovascular Score, Central Nervous System Score, Renal Score in accordance to:

Table 1. Sequential [Sepsis-Related] Organ Failure Assessment Score^a

System	Score				
	0	1	2	3	4
Respiration					
PaO ₂ /Fio ₂ , mm Hg (kPa)	≥400 (53.3)	<400 (53.3)	<300 (40)	<200 (26.7) with respiratory support	<100 (13.3) with respiratory support
Coagulation					
Platelets, ×10 ³ /μL	≥150	<150	<100	<50	<20
Liver					
Bilirubin, mg/dL (μmol/L)	<1.2 (20)	1.2-1.9 (20-32)	2.0-5.9 (33-101)	6.0-11.9 (102-204)	>12.0 (204)
Cardiovascular					
	MAP ≥70 mm Hg	MAP <70 mm Hg	Dopamine <5 or dobutamine (any dose) ^b	Dopamine 5.1-15 or epinephrine ≤0.1 or norepinephrine ≤0.1 ^b	Dopamine >15 or epinephrine >0.1 or norepinephrine >0.1 ^b
Central nervous system					
Glasgow Coma Scale score ^c	15	13-14	10-12	6-9	<6
Renal					
Creatinine, mg/dL (μmol/L)	<1.2 (110)	1.2-1.9 (110-170)	2.0-3.4 (171-299)	3.5-4.9 (300-440)	>5.0 (440)
Urine output, mL/d				<500	<200

Abbreviations: Fio₂, fraction of inspired oxygen; MAP, mean arterial pressure; PaO₂, partial pressure of oxygen.

^b Catecholamine doses are given as μg/kg/min for at least 1 hour.

^c Glasgow Coma Scale scores range from 3-15; higher score indicates better neurological function.

^a Adapted from Vincent et al.²⁷

The Modified Sequential Organ Failure Assessment (MSOFA) total score will be calculated excluding the Central Nervous System Score.

Absolute and percent changes for each including item and total score will be calculated.

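### SAP 7.7.1 leaves out the protocol's urine-output criterion for renal failure, with no entry in Section 8, so a patient who qualifies only on urine output is classed as free of organ failure

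*SAP*

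**What the plan says.** **Protocol.** Appendix 1 defines renal failure in two lists, one for patients without known chronic kidney disease and one for patients with it. Each list has four alternative criteria: a relative creatinine rise, an absolute creatinine level, "Urine output of <0.3 mL/kg/hour for ≥24 hours or anuria for ≥12 hours", and the start of renal replacement therapy. Section 8.11.5 has fluid output, comprising urine and nasogastric output, recorded at each assessment since the previous one. Weight is taken at Screening (8.1).

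**SAP.** Section 7.7.1 also has two renal lists. Each gives the two creatinine criteria and then "The initiation of renal replacement therapy". Neither mentions urine output. The section adds that patients "without data to support diagnosis of organ failure, do not have organ failure". Organ failure from 7.7 feeds the Revised Atlanta grade (7.9) and the determinant-based grade (7.10), both shown as frequency tables. The SOFA renal item in 7.8.1 does keep a row for "Urine output, mL/d".

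**Change control.** SAP Section 2 says: "Any changes from the final CSP are given in Section 8". Section 8 is a heading with nothing under it. Protocol 10.4 makes the SAP the deciding document for all statistical analyses.

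**Biomarkers.** Protocol 8.11.11 says: "Urine NGAL will also be tested". SAP 7.5.1 opens with "The following biomarkers will be used in the analyses" and lists the neutrophil/lymphocyte ratio, CRP, D-dimer, procalcitonin, IL-6 and IL-8. Urine NGAL is not there.

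**The concern.** The renal text in the SAP tracks Appendix 1 closely, list by list, except that one of the four criteria is missing from each. Nothing says whether this was decided or is a slip. Because the SAP governs, the narrower definition would be programmed. Because patients without supporting data default to no organ failure, a patient who qualifies on urine output alone becomes a definite negative, not an unknown.

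Two errors are possible. A patient may be recorded as having no organ failure at all. Or a patient whose creatinine criterion lasts less than 48 hours while low urine output continues to 48 hours or beyond may be recorded as transient when Appendix 1 would make the failure persistent. Either can lower a severity grade. The organ-failure listings (SAP 7.7.3) show only the definition variables, and urine output is no longer one of them, so those listings would not reveal the loss.

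**Working it through.** **1. The renal criteria side by side.**

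| Criterion | Protocol Appendix 1, both lists | SAP 7.7.1, both lists |
|---|---|---|
| Creatinine rise of at least 300% from a known pre-admission value | yes | yes |
| Creatinine level (at least 1.9 mg/dL; above 4.0 mg/dL with chronic kidney disease) | yes | yes |
| Low urine output or anuria | yes | **no** |
| Start of renal replacement therapy | yes | yes |

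**2. The threshold in volume.** 0.3 mL/kg/h × 24 h = 7.2 mL/kg per day. That is 432 mL at 60 kg, 576 mL at 80 kg and 720 mL at 100 kg.

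**3. An illustrative patient.** Take 80 kg, 400 mL in 24 h, creatinine 1.7 mg/dL, no chronic kidney disease, no 300% rise, no other organ-failure criterion. Since 400 < 576, Appendix 1 gives renal failure. Since 1.7 < 1.9 and there is no renal replacement, SAP 7.7.1 gives none. The same result holds at any weight above 400 / 7.2 = 55.6 kg. With chronic kidney disease the absolute creatinine cut is above 4.0 mg/dL, so more room is left for patients who qualify on urine output alone.

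**4. Effect on the grades.**
- *No complications or necrosis, urine-only failure:* mild under the SAP on both scales. Under Appendix 1, transient failure gives moderately severe (Atlanta) and moderate (determinant-based); persistent failure gives severe on both.
- *Local complications already present (Atlanta), or sterile necrosis (determinant-based):* already moderately severe or moderate. Transient oliguria changes nothing; only persistent failure moves the grade.

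**5. Size per patient.** Enrolment reproduces: 4 + 4 + 8 + 8 = 24. At 3:1 this gives 3 + 3 + 6 + 6 = 18 active and 1 + 1 + 2 + 2 = 6 control.

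| Group | One patient |
|---|---|
| Control, or first-phase active (6 each) | 1/6 = 16.7 points |
| Second-phase active (12) | 1/12 = 8.3 points |
| All active (18) | 1/18 = 5.6 points |

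**6. How likely is one such patient?** The documents give no rate. Assuming 2%, 5% or 10%, the chance of at least one among 24 is 1 − (1 − p)^24 = 38%, 71% or 92%, with 0.5, 1.2 or 2.4 expected. These rates are assumptions that show the range only.

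**7. Can the criterion be derived?** Assessments are 12-hourly on Days 1–5 (Appendix 11, note e), which suits both the 12-hour and 24-hour windows. On Days 6–10 they are 24-hourly (8.7, 8.8). A 24-hour total can support the 24-hour criterion but generally cannot show 12 hours of anuria. Section 8.11.5 describes output as a total of urine and nasogastric volume, so the case report form must hold urine separately.

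**The case against.** The strongest reply is that the protocol leaves endpoint detail to the SAP and makes it the deciding document, so a different definition is allowed. That stands. The lapse is that the SAP promises to record changes and does not record this one.

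The consequence is also limited. The study is descriptive, its primary endpoint is safety, and organ failure itself is only listed. Two secondary frequency tables can move, and only for a patient with no other feature setting the grade. SAP 4.5 also says that collected data are listed in general, so raw urine volumes may appear elsewhere. All of this stands and keeps the point modest.

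Three stronger readings are tempting, and the documents do not support them:

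- *That oliguric patients as a group are graded free of organ failure.* SAP 7.7.1 needs only one criterion of any kind. An oliguric patient who meets a creatinine, renal replacement, respiratory or cardiovascular criterion is still counted.
- *That SOFA and organ failure disagree because of the omission.* SOFA uses a fixed 500 mL per day; Appendix 1 scales with weight. They coincide at 500 / 7.2 = 69.4 kg and disagree elsewhere under the protocol's own definitions. At 60 kg, 450 mL scores SOFA renal 3 yet does not meet the 24-hour criterion (432 mL). Restoring the criterion would not remove such differences. The SOFA row shows only that the SAP expects urine output to be available.
- *That leaving out urine NGAL contributes to misgrading.* NGAL is an organ-failure criterion in neither document. SAP 3.1.4 also leaves its biomarker list open, so that gap is an inconsistency between 3.1.4 and 7.5.1 as much as an omission.

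**Conclusion.** The point holds in a limited form. SAP 7.7.1 omits an Appendix 1 renal-failure criterion from both lists, and the change is not recorded. It affects patients whose sole organ-failure criterion is urine output, or whose oliguria lasts longer than any other criterion. For them, severity may be understated in the Revised Atlanta and determinant-based tables when no other feature fixes the grade.

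The size is 5.6 to 16.7 percentage points per affected patient, depending on the group. How many there will be cannot be determined from the documents; it could be none. No sample-size or power figure is involved. The conclusion assumes that 7.7.1 will be programmed as written and that Section 8 has no content beyond its heading. It deserves correction before lock but does not threaten the primary safety objective.

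**What to change.** Before database lock, reconcile SAP 7.7.1 with Appendix 1:

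- Restore the urine-output and anuria criterion in both renal lists.
- State the derivation: recorded urine output, held separately from nasogastric output, divided by Screening weight and interval length.
- Add urine output to the definition variables listed under 7.7.3.
- State that 12-hour anuria generally cannot be derived from the 24-hourly totals on Days 6–10.

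If the removal is intended, record and justify it in Section 8 instead.

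As a separate item, add urine NGAL to the list in SAP 7.5.1 or record its removal in Section 8.

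The cost is SAP wording and modest programming. The drawback is imprecision in charted urine volumes. If the case report form holds only a combined fluid total, the criterion cannot be derived, and Section 8 should say so.

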4.8 Handling of Drop-outs, Missing Data and Outliers

Outliers will be included in summary tables and listings, and will not be handled separately in any analyses. No imputation of missing data will be performed (however, will data entered in unscheduled visit be placed to the nearest applicable visit with missing values).

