7.9 Secondary Endpoints - Revised Atlantic Classification of Acute Pancreatitis

7.9.1 Definition

Revised Atlanta Classification of Acute Pancreatitis, is determined by transient or persistent organ failure (Section 7.7), and local or systemic complications (systemic complications is defined as exacerbation of pre-existing comorbidity).

Grades of Severity	
Mild	No organ failure No local or systemic complications
Moderately Severe	Organ failure that resolves within 48 hours and/or Local or systemic complications without organ failure
Severe	Persistent Organ Failure

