7.10 Secondary Endpoints - Determinant Based Classification of Acute Pancreatitis

7.10.1 Definition

Severity as defined by Determinant Based Classification of Acute Pancreatitis will be provided by CalciMedica in excel format in accordance to by subject:

	Mild AP	Moderate AP	Severe AP	Critical AP
(Peri)pancreatic necrosis	No	Sterile	Infected	Infected
	And	And/Or	Or	And
Organ Failure	No	Transient	Persistent	Persistent

The Excel file will have information regarding: Randomization number, outcome of (Peri)pancreatic necrosis. Organ failure will be captured in accordance with section 7.7.

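### SAP 7.7.1 counts absent organ-failure data as no organ failure; the two severity tables it feeds have no not-assessable category, and the 48-hour threshold has no rule for gaps

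*SAP*

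**What the plan says.** SAP 7.7.1, under Any Organ Failure, states that patients free of every type of organ failure "or without data to support diagnosis of organ failure, do not have organ failure". The sentence is about patients, not days.

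The next paragraph of 7.7.1 deals with duration: "Patients with transient organ failure are identified by organ failure lasting less than 48 hours", and "Persistent organ failure is documented for greater or equal to 48 hours". It does not say how duration is built from scheduled readings, or what a missing reading does to an episode.

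This status is then used twice. The Revised Atlanta grade "is determined by transient or persistent organ failure (Section 7.7), and local or systemic complications" (SAP 7.9.1). For the determinant-based grade, "Organ failure will be captured in accordance with section 7.7" (SAP 7.10.1), with necrosis as a separate input supplied by the sponsor. Both grades are shown in frequency tables (7.9.3, 7.10.3), and neither section mentions patients who cannot be graded. The organ-failure variables themselves appear only in listings, with their defining variables (7.7.3).

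The general rule in SAP 4.8 is "No imputation of missing data will be performed". Its one exception lets data from an unscheduled visit fill the nearest visit with missing values.

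**The concern.** The no-data clause is an imputation of the best outcome, under a different name from the one 4.8 excludes. It works in one direction only: absent data can remove an organ failure from the grade and can never add one. A reader of the 7.9 or 7.10 table sees a Mild or Moderate count and cannot tell patients shown to be free of organ failure from patients whose failure was not captured.

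The silence on gaps adds to this. Persistent organ failure is what makes a patient Severe under Atlanta, and it is one of the two routes to Severe in the determinant-based scheme. If programmers carry the no-data clause down to single days, a lost reading can end an episode early. In arms this small, one such patient is visible in the percentages, and with descriptive tables only, no model or sensitivity analysis would correct it.

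**Working it through.** **1. Arm sizes.** The cohorts in SAP 3.2 are 4 + 4 + 8 + 8 = 24, which reproduces the stated sample size. At 3:1:
- supportive care: 1 + 1 + 2 + 2 = 6
- lower dose: 3 + 3 = 6
- higher dose: 6 + 6 = 12

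**2. Weight of one patient.** 1/6 = 16.7 percentage points, 1/12 = 8.3, and in pooled active 1/18 = 5.6.

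**3. Effect on the grade, from the tables in SAP 7.9.1 and 7.10.1.**

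| True organ failure | Taken as | Revised Atlanta | Determinant-based |
|---|---|---|---|
| Persistent | None | Severe to Mild (no complication recorded) or to Moderately Severe (complication recorded) | Severe to Mild (no necrosis) or to Moderate (sterile necrosis); Critical to Severe (infected) |
| Persistent | Transient | Severe to Moderately Severe | Severe to Moderate; Critical to Severe (infected) |

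Every change is downward.

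**4. Where gaps can arise.** Organ failure is assessed on Days 1-10 (Protocol Appendix 1). Protocol creatinine comes from a chemistry profile drawn once daily and sent to the central laboratory (Protocol 8.11.9), and SpO2 with FiO2 is scheduled once daily. Vital signs are 12-hourly on Days 1-5 (Protocol Appendix 11).

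**5. One missing day in an episode.** Assumption: a missing day is read as no failure. The main reading takes 48 hours as three consecutive positive daily readings (0, 24 and 48 h). The variant takes it as two calendar days. For an episode of L positive readings, count the positions at which losing one reading turns persistent into transient.

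| L | Three readings needed: missing = no failure | Three readings needed: interior gap bridged | Two days needed: missing = no failure | Two days needed: interior gap bridged |
|---|---|---|---|---|
| 2 | not persistent | not persistent | 2 of 2 | 2 of 2 |
| 3 | 3 of 3 | 2 of 3 | 1 of 3 | 0 of 3 |
| 4 | 2 of 4 | 0 of 4 | 0 of 4 | 0 of 4 |
| 5 | 1 of 5 | 0 of 5 | 0 of 5 | 0 of 5 |
| 6 or 7 | 0 | 0 | 0 | 0 |

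Illustration: creatinine 2.5 mg/dL on Day 3 (48 h), missing on Day 4, and 2.5 on Day 5 (96 h), against the 1.9 mg/dL criterion. The outer readings are 96 − 48 = 48 h apart. With the gap bridged, the episode is persistent. With the gap read as no failure, it is two shorter episodes and the Atlanta grade falls by one level.

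**6. How often a gap might occur.** The documents give no rate. Assuming independent missingness m per reading, the chance of at least one gap in three readings is 1 − (1 − m)³:
- m = 2%: 5.9%
- m = 5%: 14.3%
- m = 10%: 27.1%
- m = 20%: 48.8%

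**7. Truncation.** SAP 7.7.1 defines transient failure by observed length alone, whereas the middle row of the Atlanta table in 7.9.1 speaks of failure that resolves. A patient still in failure who dies or withdraws before 48 hours fits the 7.7.1 wording for transient although nothing resolved.

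**The case against.** A good deal can be said for the plan.

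- A reader might infer that unassessed patients are automatically graded Mild. The documents do not support that. Mild also requires no local or systemic complication (Atlanta) or no necrosis (determinant-based), and CT findings can raise the grade on their own. A wholly unassessed patient is also unlikely, because vital signs, blood sampling and SpO2/FiO2 on Day 1 precede randomization (Protocol 8.2 and Appendix 11).
- A reader might infer that the SAP makes a missing day convert persistent failure to transient. It does not say so. The no-data sentence is written for patients, and the duration paragraph is silent. The conversion is one possible consequence of an unstated rule, and under the readings above it affects only short episodes.
- A reader might infer that one lost creatinine sample leaves the kidney unassessed that day. Renal replacement therapy started since the prior assessment is recorded (Protocol 8.11.5), as are ventilation and vasopressor starts for the other two systems. An unscheduled value may also fill the gap under SAP 4.8.
- A reader might infer that the rule hides the sickest patients. The documents give no pattern of missingness. After Day 5, assessments apply only to patients still in hospital (Protocol 8.7), so the built-in source of absent data is discharge. Deaths are listed (SAP 7.13.3), and organ-failure listings show the defining variables.
- The visit windows are ±1 hour, so Day 3 to Day 5 readings can be 46 to 50 hours apart. The 48-hour example can fail on actual times even with complete data.
- These are secondary, untested, descriptive endpoints in an unpowered study whose primary objective is safety.

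All of this stands, and it limits the point. It does not remove the written clause, its one-way effect, or the absence of any sign of it in the two severity tables.

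**Conclusion.** The concern holds in limited form. SAP 7.7.1 treats absent organ-failure data as absence of organ failure. For in-hospital gaps this can only lower the organ-failure component of two tabulated severity grades, and a Mild grade follows when no complication or necrosis is recorded either. Separately, the SAP has no rule for a missing in-hospital day, or for follow-up cut short by death or withdrawal, when the 48-hour threshold is applied.

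Each regraded patient moves a category by 16.7 points (arms of 6) or 8.3 points (arm of 12). How many patients would be regraded cannot be derived, because the documents give no missing-data rate. The range of about 3 to 5 daily readings for vulnerable episodes assumes that a missing day is read as no failure and that 48 hours means three consecutive daily readings. With two calendar days it is 2 to 3. The change is worth making before the SAP is signed, but it does not touch the primary safety objective.

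**What to change.** Delete the no-data limb of the sentence in SAP 7.7.1 and add:

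> Organ failure is evaluated on study days in hospital up to Day 10; days after discharge are not counted as missing. A patient who meets no criterion on any in-hospital day, and for whom one or more organ systems has no data on one or more in-hospital days after using unscheduled values per Section 4.8, is shown as organ failure not assessable. A missing in-hospital day between two days of failure of the same organ does not end the episode. Failure still present at the last available assessment before death or withdrawal, with less than 48 hours observed, is shown as duration not determinable rather than transient.

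Add both statuses as rows, with n, to the 7.9 and 7.10 tables. Show the same tables under the current SAP rule as a sensitivity display. Limiting the rule to in-hospital days matters: otherwise recovered patients discharged before Day 10 would drop out of Mild.

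Two limits should be stated openly. Bridging an interior gap is itself a form of imputation, so 4.8 should name it as an exception. It also does not rescue a gap at the first or last reading, which still converts a three-reading episode in 2 of 3 positions.

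The cost is SAP wording, a little more programming and somewhat less complete tables; no new data are needed. The size of the not-assessable row depends on the unknown missing-data rate, and the display under the current rule lets readers see how much it matters.
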